10.3 Eliciting adverse event information

Safety events will be recorded from the time the participant signs the informed consent form until 48 hours after the last study visit. For participants in the active control group who take up the offer to complete the TALI program, safety events will be recorded until the tablet provided with the TALI program has been returned. At each point of contact with participants caregivers, researchers will enquire as to how the participants has been since their last contact in order to elicit any changes in their wellbeing. At each study visit participants and their parent/caregiver will be asked "How have you felt since your last visit?" in order to elicit any changes in their wellbeing.

10.4 Serious adverse event reporting

10.4.1 SAES

Any SAE occurring in a study participant will be reported to the HREC within 24-72 hours of occurrence, in accordance with the safety reporting policy of the HREC. The HREC safety reporting form will be completed, signed and submitted by an investigator.

11 DATA MANAGEMENT

11.1 Data Collection

The investigators are responsible for ensuring the accuracy, completeness, legibility, and timeliness of the data reported. All source documents should be completed in a neat, legible manner to ensure accurate interpretation of data. The investigators will maintain adequate case histories of study participants, including accurate case report forms (CRFs), and source documentation.

11.1.1 Source Data

Source data will include original records in medical records and research initiated data. Access to EMR will be restricted to those investigators who have received training and undergone relevant criminal records checks.

11.1.2 Data Capture Methods

Paper and electronic data will be collected. All electronic data will be stored in a password secured study database (REDCap), accessible at Monash University and MCRI. Deidentified data files will be stored on a password protected computer within the Monash University lab, and on an encrypted, password protected USB.

11.2 Data Storage

All data collected will be entered into a password protected study database (REDCap) by individuals in the research team, and will be identified by a unique study identification number (created for each participant at the time of recruitment). Identifiable data, such as names and contact details, will be kept in a separate section of the database with restricted access, which can only be accessed by specific members of the research team (i.e. investigators). All paper based data will be stored in participant files (CRFs) in secured filing cabinets at the Murdoch Children's Research Institute.

The information collected from this study will only be available to members of the research team involved in this study. In the event that a caregiver (i.e. parent or guardian) request for certain information or summary reports of cognitive assessment to be provided to a third party (e.g. school teacher, paediatrician), a Permission to Share Information form will be completed and signed by the caregiver in order for the study information to be released and shared. All members of the research team, including students, are trained in confidentiality.

11.3 Record Retention

Storage of the data collected will adhere to the Monash University regulations and will be kept on University premises in a locked filing cabinet until the 25th birthday of the youngest participant in accordance with the requirements of the Health Privacy Principles. Electronic information will be stored on a password protected computer.

These research records will not be made available to any individuals who are not part of the research team unless requested by the caregiver or required by law. As the lead researcher ([name]) is located at Monash University, participant files will be transported to Monash University in a secure document case following the completion of the study. Files will be stored in the School of Psychological Sciences at Monash University in locked filing cabinets, accessible only by members of the research team, until such time (as stated above) that they may be confidentially destroyed.

Paper-based information collected as part of this study will be destroyed after the above stated timeframe has lapsed. All documents will be disposed of in a secure document disposal bin. De-identified electronic data collected both directly and derived from the paper-based information will be kept indefinitely for future analyses.

12 STUDY OVERSIGHT

12.1 Governance structure

This project will sit within the Monash University School of Psychological Sciences and the Murdoch Children's Research Institute. Therefore, governance will sit within these existing structures. A specific steering committee is not required.

12.2 Quality Control and Quality Assurance

The Quality Control and Quality Assurance guidelines will be detailed in the standard operating procedures (SOP) document.

- Staff contacting families for screening or contact at the time of baseline and follow-up assessments will be trained by the study co-ordinator.
- Compliance with the study protocol will be assessed by the study co-ordinator monthly
- To ensure a high degree of proficiency, staff providing interventions will receive clinical neuropsychology training to a level consistent with AHPRA regulations.

13 STATISTICAL METHODS

13.1 Sample Size Estimation

A priori power analysis using G*Power 3.1 estimated a required sample between 40 (for a large effect size) and 98 (for a medium effect size) participants based on the following parameters:

- ANOVA: repeated measures between factors
- estimated effect size f .4 (large) and .25 (medium)
- alpha .05
- power .8
- Number of groups: 2
- Number of measurements: 2
- Correlation among measures: .5

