5 PARTICIPANTS AND RECRUITMENT

5.1 Number of Participants

This study will aim to recruit 80 participants, 40 per group. Participants will comprise children with an ABI. Participants will be recruited through the Victorian Paediatric Rehabilitation Service Database and review of medical records.

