9 OUTCOMES

9.1 Primary outcome

The primary outcome is an improvement in cognitive attention, as measured by the Test of Everyday Attention for Children (selective and sustained attention) and experimental paradigms of attentional control (interference control with the Child ANT test and response inhibition with the anticipated response task) between the intervention and control group at post-training.

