13.2.3 Methods of analysis

Primary outcome measure

To meet the primary objective of the study, the four primary outcome measures: response inhibition, interference control, selective attention, and sustained attention as measured by the Anticipated Response task, Child ANT, and TEA-Ch 2 respectively, will be analysed using Latent Growth Curve Modelling (LGCM) using a multigroup approach. An alpha level of .05 and two-tailed tests will be used for this analysis. LGCM will be conducted through R. Participants will be compared to their own baseline at each of the three subsequent testing time points, and further comparisons will be made between time points (e.g. 5 week follow up and 3 month follow up, 5 week follow up and 6 month follow up). Participants in the TALI program group and the active contact group will also be compared at each time point. LGCM will allow for baseline ability to be taken into consideration.

Secondary outcomes measures

To meet the secondary objective of determining whether improvements in cognitive attention transfer to improvements in other domains including mathematics ability, working memory and social functioning in children with ABI who complete the TALI attentional training program, further LGCM will be used as described above with the secondary outcome variables listed in section 9.2.

Additional analysis

To meet the secondary objective of identifying factors which predict improvement in attention in children with ABI who complete the TALI attentional training program, LGCM will be used. Predictor variables will be obtained through data collected from the demographic screening survey including age at time of injury, type of injury, length of time since injury, severity of attentional deficits and socio-economic background, as well as from data obtained through assessment measures relating to motivation, sleep, mental health and family functioning.

To meet the final secondary objective of investigating whether there are differences in the types of attentional deficits found in typically developing children, when compared with children with ABI, children's scores on the Connor's EC/3 will be compared using an independent samples, two-tailed ANOVA with an alpha level of .05

Data on typically developing children will be obtained from previous study database, whereby participants consented to their de-identified data being used for further research.

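### Section 13.1 powers a time-averaged group difference instead of post-training change, and ties the planned 80 children to no effect size

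*Protocol*

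**What the plan says.** Protocol section 13.1 reports that an a priori G*Power calculation "estimated a required sample between 40 (for a large effect size) and 98 (for a medium effect size) participants". The listed settings are "ANOVA: repeated measures between factors", f of .4 and .25, alpha .05, power .8, "Number of groups: 2", "Number of measurements: 2" and a correlation of .5 among measures. It does not name the two measurements.

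Section 5.1 sets the size: "This study will aim to recruit 80 participants, 40 per group". The synopsis gives the same number. Neither place says which effect 80 children are meant to detect, or with what power.

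The synopsis defines the primary outcome as change in cognitive attention, and section 9.1 as improvement, in both cases compared "between the intervention and control group at post-training". Section 13.2.3 plans a multigroup latent growth curve model over the four time points that takes baseline ability into account. It adds: "An alpha level of .05 and two-tailed tests will be used for this analysis".

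**The concern.** Two things do not fit together.

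First, the between-factors option in a repeated-measures ANOVA tests whether the arms differ on the mean of all measurements. The trial's question is whether they differ in change by post-training. An f value that is medium on the first scale need not be medium on the second.

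Second, the calculation offers 40 or 98, and the trial enrols 80 without explaining the step from one to the other. Since .8 is the only power printed, a reader may carry it over to 80 children and treat a null result as evidence against a medium effect. The section also makes no allowance for children lost before the post-training visit, although section 8.9.2 provides for missed assessments and losses.

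**Working it through.** **Inputs.** From section 13.1: k = 2 groups, m = 2 measurements, correlation ρ = .5, alpha .05, power .8, f = .4 and .25. From section 5.1: N = 80, 40 per arm. From section 13.2.3: two-sided tests.

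**Step 1. Reproduce 40 and 98.** For the between-factors test the noncentrality is λ = f²·N·m / [1 + (m − 1)ρ], with 1 and N − 2 degrees of freedom.

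- f = .4, N = 40: λ = .16 × 40 × 2 / 1.5 = 8.53, power .812. N = 38 gives .791.
- f = .25, N = 98: λ = .0625 × 98 × 2 / 1.5 = 8.17, power .808. N = 96 gives .799.

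Both stated figures reproduce exactly. With the same f values, the within-between interaction, λ = f²·N·m / (1 − ρ), would give 16 and 34. The between-factors label is therefore what was computed, not a slip of wording.

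**Step 2. The planned 80 on the same formula.**

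- f = .25: λ = .0625 × 80 × 2 / 1.5 = 6.67, power .722.
- f = .4: λ = .16 × 80 × 2 / 1.5 = 17.07, power .983.
- Power .8 is reached at f ≈ .275.

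This step needs no assumption about what the two measurements are.

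**Step 3. What the tested effect means.** Assume the two measurements are baseline and post-training. Randomisation makes the expected baseline difference zero. If the post-training difference is d (in SD units), the averaged difference is (0 + d)/2 = d/2. With two groups, f is half the standardised averaged difference, so f = d/4. A post-training difference of 0.5 SD therefore enters this test as f = .125, not .25.

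**Step 4. What 80 children can detect at post-training.** For a comparison adjusted for baseline, λ = d²·(N/4) / (1 − r²), where r is the baseline to post-training correlation and the test has N − 3 degrees of freedom. The protocol gives .5 for r; .3 and .7 are assumed here to show the range.

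| r | λ at d = 0.5, N = 80 | Power for 0.5 SD | d detectable with 80% power |
|---|---|---|---|
| .3 | 5 / .91 = 5.49 | 64% | 0.61 SD |
| .5 | 5 / .75 = 6.67 | 72% | 0.55 SD |
| .7 | 5 / .51 = 9.80 | 87% | 0.45 SD |

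With an assumed loss of 10% (72 analysed) or 20% (64 analysed) and r = .5, power for 0.5 SD is 68% or 62%.

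**The case against.** The arithmetic in section 13.1 is right for the test it names. That stands: the weakness is the choice of test and the unexplained 80, not a miscalculation.

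A reader might infer that the protocol misstates its power, promising 80% for a medium effect and delivering 72%. The text does not support this. It says a medium effect needs 98 and plans 80, so the shortfall is visible on the page. Most of the f range from .25 to .4 is covered at .8 or better.

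A reader might also go on from Step 3 to say that the trial is sized for post-training differences of 1.0 SD (4 × .25) and 1.6 SD (4 × .4), or that 80 children have only 25% power for 0.5 SD. Those figures are correct for the named test if its measurements are baseline and post-training. But that reading is inferred, and no one plans to run that test: the analysis is a latent growth curve model that uses baseline.

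Nor does the mismatch show that 98 is too small. At ρ = .5 the variance factor of the averaged test, (1 + ρ)/2 = .75, happens to equal the baseline-adjusted factor, 1 − ρ² = .75. The totals 40 and 98 therefore also suit a baseline-adjusted post-training comparison at d = .8 and d = .5. This coincidence holds at .5 but not in general, the section does not describe such a comparison, and 80 children still give 72% at d = .5.

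The four-point growth model might gain precision over a two-point comparison. The protocol gives no calculation for that.

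**Conclusion.** The point holds as a fault in the sample-size justification, not in the arithmetic. The section powers a time-averaged group difference, whereas the primary outcome is the post-training difference in change. The planned 80 is linked to no effect size. On the protocol's own formula it gives 72% at f = .25 against the only stated power of .8.

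The 72%, 98% and f ≈ .275 figures rest on the protocol's inputs alone. The halving in Step 3 depends on the two measurements being baseline and post-training. The detectable differences depend on the correlation and on using a baseline-adjusted comparison as an approximation to the post-training contrast from the growth model. The loss rates are assumptions.

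It should be fixed, because the section is wrong as written. The number of children and the analysis need not change. How to handle four primary measures at alpha .05 is a separate question and is not counted here.

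**What to change.** Keep 80 children. Remove the between-factors calculation and the 40 to 98 range from section 13.1, and state what 80 can detect at post-training. For example:

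*With 80 children and two-sided alpha .05, a baseline-adjusted post-training comparison has 80% power for 0.55 SD if the baseline correlation is .5 (0.61 SD at .3, 0.45 SD at .7), and 72% power for 0.5 SD (64% at .3, 87% at .7). With an assumed 10–20% loss and correlation .5, power for 0.5 SD is 68–62%. This comparison approximates the post-training contrast from the planned latent growth curve model.*

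Do not simply switch the G*Power option to the interaction at the same f values. That would return 34 and 16, because f has a different meaning there; the effect has to be restated as a post-training difference.

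The cost is a text amendment. No extra children are needed.

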13.2 Statistical Analysis Plan

Primary outcome – Cognitive attention: selective attention, sustained attention, response inhibition, and interference control

- Mean scores for selective and sustained attention, response inhibition and interference control for the intervention and control groups, across each time point will be presented.
- Latent Growth Curve Modelling will be used to analyse the difference in scores both within and between the intervention and control group, across all four time points.

Secondary outcomes – (include) behavioural attention, working memory, social skills, and mathematic ability

- Mean scores for each variable, for each group, across each time point will be presented.
- Latent Growth Curve Modelling will be used to analyse the difference in scores on the above variables both within and between groups, across all four time points.

13.2.1 Population to be analysed

An intention to treat approach will be taken, where all children enrolled in the trial will be analysed.

13.2.2 Handling of missing data

Prior to investigating treatment effect, analyses will assess whether children who did not adhere to the program (<20 sessions) differed from those who did adhere to the program (>20 sessions).

Statistical methods that will be used to handle missing data will depend on the amount of missing data and the pattern of missing data. These methods will include either regression methods of imputation in cases where missing data is <20% and Missing Completely at Random, or in cases where missing data is Missing at Random, Expectation Maximisation method of data imputation will be used.

13.2.3 Methods of analysis

Primary outcome measure

To meet the primary objective of the study, the four primary outcome measures: response inhibition, interference control, selective attention, and sustained attention as measured by the Anticipated Response task, Child ANT, and TEA-Ch 2 respectively, will be analysed using Latent Growth Curve Modelling (LGCM) using a multigroup approach. An alpha level of .05 and two-tailed tests will be used for this analysis. LGCM will be conducted through R. Participants will be compared to their own baseline at each of the three subsequent testing time points, and further comparisons will be made between time points (e.g. 5 week follow up and 3 month follow up, 5 week follow up and 6 month follow up). Participants in the TALI program group and the active contact group will also be compared at each time point. LGCM will allow for baseline ability to be taken into consideration.

Secondary outcomes measures

To meet the secondary objective of determining whether improvements in cognitive attention transfer to improvements in other domains including mathematics ability, working memory and social functioning in children with ABI who complete the TALI attentional training program, further LGCM will be used as described above with the secondary outcome variables listed in section 9.2.

Additional analysis

To meet the secondary objective of identifying factors which predict improvement in attention in children with ABI who complete the TALI attentional training program, LGCM will be used. Predictor variables will be obtained through data collected from the demographic screening survey including age at time of injury, type of injury, length of time since injury, severity of attentional deficits and socio-economic background, as well as from data obtained through assessment measures relating to motivation, sleep, mental health and family functioning.

To meet the final secondary objective of investigating whether there are differences in the types of attentional deficits found in typically developing children, when compared with children with ABI, children's scores on the Connor's EC/3 will be compared using an independent samples, two-tailed ANOVA with an alpha level of .05

Data on typically developing children will be obtained from previous study database, whereby participants consented to their de-identified data being used for further research.

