7 RANDOMISATION AND BLINDING

A statistician not directly involved in the analysis of the study results will prepare the randomisation schedule using block randomisation (ratio 1:1, blocks of 4) to maintain balance between intervention arms. The randomisation will be stratified by injury severity with three strata: mild, moderate to severe, and other (where injury severity cannot be classified). Computer-generated random numbers will be used to allocate participants.

The documentation pertaining to the randomisation will be securely stored and inaccessible to researchers undertaking recruitment and testing.

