8.5 Visits

Visit 2, Week 6 ± 1 week

Participants may find the assessment sessions to be tiring and small breaks should be provided when needed. Children will be asked to complete:

1. Stanford Sleepiness Scale
2. Tea-Ch2 selective and sustained attention subtests
3. Child ANT and Anticipated Response Task

Break if needed

4. Corsi Block-Tapping Test
5. Digit Span task

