1. SWAN
2. CSHQ
3. PECCI
4. GHQ-12
5. CDS-P
6. SCAS-P
7. PEERS-Q

8.6 Final study visit

Visit 4, Week 26 ± 1 week

Participants may find the assessment sessions to be tiring and small breaks should be provided when needed. Children will be asked to complete:

1. Stanford Sleepiness Scale
2. Tea-Ch2 selective and sustained attention subtests
3. Child ANT and Anticipated Response Task

Break if needed

4. Corsi Block-Tapping Test
5. Digit Span task

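### The primary outcome is the arm difference at post-training, but the analysis section neither designates that contrast as primary nor fixes the curve shape and baseline constraint

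*Protocol*

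**What the plan says.** The synopsis and section 9.1 define the primary outcome as cognitive attention compared "between the intervention and control group at post-training". In the visit schedule (section 8.5) that is "Visit 2, Week 6 ± 1 week".

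Section 13.2 applies latent growth curve modelling to differences "both within and between the intervention and control group, across all four time points". The last of these is "Visit 4, Week 26 ± 1 week" (section 8.6). Section 13.2.3 repeats that the four primary measures "will be analysed using Latent Growth Curve Modelling (LGCM) using a multigroup approach", with two-sided tests at .05. Under the same heading it lists three families of comparison:

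- "Participants will be compared to their own baseline at each of the three subsequent testing time points";
- comparisons of one follow-up visit with another;
- the two arms against each other at every time point.

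The section adds that the model takes baseline ability into account, without saying how. It gives no growth shape, no time coding and no primary parameter or contrast.

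Section 7 states: "The randomisation will be stratified by injury severity with three strata". Injury severity is not mentioned in section 13.2 or 13.2.3.

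**The concern.** The protocol fixes one time point for its primary outcome and then fixes a model family and a set of comparisons that do not single that time point out. Training lasts five weeks, and section 8.11 withdraws access to the program afterwards. The natural pattern for a real effect is therefore a rise by week 6 that then holds or fades. If the reported result were a growth-rate difference over 26 weeks, it would answer a different question, and a real post-training benefit could be missed because it did not keep growing.

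Leaving the contrast open also allows it to be chosen after the data are seen, from comparisons that would each be tested at .05.

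The own-baseline comparisons add to the ambiguity because they stand among the analyses for the primary objective. Section 3.1 states that objective as a comparison with children doing a control task. Children sit the same tests four times while they mature, so change within one arm cannot be attributed to training.

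**Working it through.** **The plan's own figure.** Section 13.1 uses a repeated-measures ANOVA, between factors, with m = 2 measurements, ρ = .5, alpha .05 and power .8. The noncentrality is λ = f²·N·m / [1 + (m−1)ρ], with 1 and N−2 degrees of freedom.

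- f = .40, N = 40: λ = .16×40×2/1.5 = 8.53, power 81.2%.
- f = .25, N = 98: λ = .0625×98×2/1.5 = 8.17, power 80.8%.

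Both stated sample sizes reproduce. At the planned N = 80 the same formula gives 72% for f = .25 and 98% for f = .40. That test averages two measurements, so it corresponds neither to a four-visit growth curve nor to a Visit 2 contrast.

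**Assumptions for the comparison.** From the protocol: N = 80 (40 per arm), ρ = .5, two-sided .05. Not in the protocol, and assumed here: SD 1, equal correlation between all visits, no dropout, visits coded 0, 6, 13 and 26 weeks, a straight-line growth factor, and a true arm difference of 0.55 SD at week 6. Three later patterns were tried: held (0, 1, 1, 1 × 0.55), halved by week 26 (0, 1, .75, .5 × 0.55) and gone by week 26 (0, 1, .5, 0 × 0.55). Power uses the noncentral t.

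**Visit 2 contrast.**

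- Baseline constrained or adjusted: variance 1 − ρ² = .75; SE = √(.75×4/80) = .194; ratio .55/.194 = 2.84; power .80.
- Change score: variance 2(1−ρ) = 1; SE = √(4/80) = .224; ratio 2.46; power .68.

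**Straight-line slope, baselines free.** Mean time is 45/4 = 11.25, and the sum of squares about it is 881 − 4×11.25² = 374.75. The slope SE is √[(.5/374.75)×4/80] = .00817 per week.

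- Held: .55×11.25/374.75 = .0165; ratio 2.02; power .51 (.52 by normal approximation).
- Halved: .55×3.4375/374.75 = .0050; ratio 0.62; power .09.
- Gone: .55×(−4.375)/374.75 = −.0064. The expected slope difference is negative.

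**Straight-line slope, baselines equal.** The inverse covariance matrix is 2(I − .2J), so the information is 2(881 − .2×45²) = 952, and the SE is √[(1/952)×4/80] = .00725.

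- Held: 2(24.75 − 14.85)/952 = .0208; ratio 2.87; power .81.
- Halved: 2(15.8125 − 11.1375)/952 = .0098; ratio 1.36; power .27.
- Gone: 2(6.875 − 7.425)/952 = −.0012, again negative.

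**What a straight line reports at week 6.** With a true difference of 0.50 SD and free intercepts, the fitted week-6 difference is 0.30 (held), 0.26 (halved) or 0.22 (gone). Between 0.21 and 0.25 SD is absorbed as a baseline difference that does not exist.

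**A growth curve with a knot at week 6 and equal baselines.** At 0.55 SD, power for the week-6 difference is about .87 (held), .85 (halved) and .83 (gone), against .80 for the categorical contrast.

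**The case against.** Four points on the other side have force.

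1. A reader might infer that the plan never compares the arms at post-training. It does: section 13.2.3 compares them at each time point, and Visit 2 is one of these. What remains is that this comparison is one of many and is not marked as primary.

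2. A reader might infer that the multigroup model frees the baseline means. That is a usual default, but the protocol does not say it, and intercepts can be constrained equal across groups. It matters for the arithmetic: .80 for a constrained Visit 2 contrast against .51 for a free-baseline slope is not like for like. With equal baselines and a held effect, the slope test reaches .81 and nothing is lost. The loss then appears only if the effect fades.

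3. A reader might infer that the analysis ignores the randomisation stratum. This rests on silence, and a covariate list commonly sits in a statistical analysis plan, which is not shown here. The same goes for age, and section 8.4 notes that the TEA-Ch2 yields scaled as well as raw scores. Neither omission is a demonstrated error, and no precision loss from either was calculated.

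4. The power losses need a straight line, which the protocol never specifies. A piecewise or free-shape growth curve recovers the post-training difference. Nor does parameter count tell against growth modelling: a linear two-group version has about 18 parameters, and a categorical-visit model with unstructured covariance and these covariates has about 20.

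It can also be said that the protocol never claims own-baseline change proves efficacy. That is true, but it lists those comparisons among the analyses meeting the primary objective, so their standing should be stated.

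**Conclusion.** The point holds as a mismatch between the outcome definition and the analysis section. The protocol fixes post-training as the primary time point, then commits to a model and a list of comparisons without naming the Visit 2 arm contrast as primary or settling the curve shape and baseline constraint. An unseen analysis plan might fill these gaps, but the text as it stands permits a primary result that is not the primary outcome.

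The size is conditional. Under a straight line and the assumptions above, slope-test power ranges from .09 to .81 when the effect holds or halves, and the expected slope is negative if the effect is gone by week 26. A baseline-constrained Visit 2 contrast has .80 throughout. Under a knot or free time scores there need be no loss. The documents do not support the broader conclusion that latent growth curve modelling is the wrong method. The fault is the undesignated contrast and the open shape.

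**What to change.** In section 13.2.3, name the arm difference at Visit 2 as the primary contrast for each primary measure. Estimate it from one model fitted to both arms, with a common baseline mean and either visit as a categorical factor or a growth curve with free time scores or a knot at Visit 2. Growth modelling may be kept.

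Include the injury-severity randomisation stratum as a covariate, and age where raw scores are analysed. Report weeks 13 and 26 from the same model as secondary estimates, and own-baseline comparisons as descriptive only. Align the wording of section 13.2 with this.

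The cost is a wording change and a few degrees of freedom. Baseline scores, stratum and age are already collected, and no visit or measurement is added.
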